7.2 PHASE II COMPONENT

Time to progression and overall survival will be evaluated using the Kaplan-Meier product-limit survival curve methodology. Six-month Progression Free Survival (PFS) will be estimated using Kaplan-Meier estimates and associated two-sided 95% confidence intervals.

- **Group A: Recurrent glioblastoma with no prior exposure to bevacizumab cohort:** A maximum of 34 patients will be observed in a two-stage Simon optimum design. In the first stage, 9 patients will be accrued. If two or more patients are progression-free at 6 months (PFS6), an additional 25 patients will be accrued. We halt registering patients after 9 patients until we have at least 2 patients are progression free at six months. If 9 or more out of 34 have PFS6, then the study will be declared

promising. This study has a 5% chance of declaring promise if the PFS6 rate is at most 15%. It has an 80% chance of declaring promise if the PFS rate is at least 35%.

- **Group B: Recurrent glioblastoma with prior exposure to bevacizumab cohort:** In the group that failed bevacizumab, a maximum of 32 patients will be observed in a two-stage Simon optimum design. In the first stage, 14 patients will be accrued. If one or more patients is progression-free at 3 months (PFS3), an additional 18 patients will be accrued. We will halt registration after 14 patients until at least 1 patient is progression free at 3-months. If 2 or more out of 32 have PFS3, then the study will be declared promising. This study has a 5% chance of declaring promise if the PFS3 rate is at most 1%. It has an 80% chance of declaring promise if the PFS rate is at least 12%.
- **Group C:** A third cohort consisting of 16 patients with **anaplastic glioma** (as defined in section 2.1.1.1) will enroll independently but will not be included in the primary endpoint assessment.

The Phase II Multicenter component of the trial will be monitored by the Study Chair, [name], and the study statistician, [name], as described below.

At phase II, we will monitor the toxicity based on the combined data from the above three cohorts with a total sample size of 82. All grade 3 or greater toxicities attributable to the study treatment in the first 28-day cycle will be counted. Accrual will be temporarily suspended for analysis after each of the following interim accrual goals. We will monitor the toxicity when the accrual is 5, 10, 20, 35, 50 and 65 based on using the following stopping rule: if the posterior probability of toxicity greater than 0.3 is greater than 0.95 (i.e., $\Pr(\text{toxicity} > 0.3 | \text{data}) > 0.95$), we terminate the study for toxicity. Assuming the beta prior $\text{Beta}(0.6, 1.4)$ for the toxicity, we have the following operating characteristics.

Operating characteristics of the proposed stopping rule

True toxicity probability	0.2	0.3	0.4	0.5
Stopping Probability	1.4%	14.1%	64.6%	97.2%
Average number of patients treated	82	74.9	49.9	24.9

We obtain the following stopping boundary: the study will be terminated if we observe $\geq 4/5$, $6/10$, $10/20$, $16/35$, $21/50$, $26/65$ (# of patients experienced DLTs/# of patients treated). Note that our safety monitoring starts with a small cohort size of 5, and then gradually increases to 15. Therefore, if the treatment agents are overly toxic, the trial will stop before exposing many patients to toxicities.

Patient-reported outcomes: The sample size for this trial was based on the primary end point of the study.

Received MDASI-BT forms will be checked versus the timing schedule and considered as valid if they fall within ten days of the scheduled assessment. Compliance rates will be calculated as the number of received valid forms over the number of expected forms. Differences between groups in compliance will be tested by use of Fisher's exact test at every time point.

We will use descriptive statistics to describe how patients rate symptom severity and interference with function at each time point. Error bar graphs for each of the symptoms will be constructed at

each time point. The proportion of patients rating their symptoms to be 7 or greater (on a 0-10 scale) will also be reported. We will construct individual patient profiles for each of the selected symptoms to describe the individual patients' patterns of change over time. We will calculate the mean core symptom severity, mean severity of the MDASI-BT and mean symptom interference at the time of clinical evaluation. Estimates of differences in the mean symptom severity and mean symptom interference between responders and non-responders will be estimated in the intent to treat population. All patients with at least one valid questionnaire will be included in the analyses. Questionnaires completed at study registration will be considered baseline. All questionnaire data received after randomization will be used in the primary analyses.

Differences of at least 2 points will be classified as the minimum clinically meaningful change in the symptom severity and symptom interference measures. For example, an increase of 2 points or more would mean a moderate improvement, whereas a decrease of 2 points or more would be interpreted as moderate worsening. For individual symptoms, a rise in a symptom score means deterioration, whereas a reduced score means improvement of the specific symptom.

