1.1.2 Phase II

1.1.2.1 Primary endpoints:

- 6 month progression free survival rate for glioblastoma patients with no prior bevacizumab exposure treated with everolimus and sorafenib at the maximum tolerated dose as determined in the phase I study.
- 3 month progression free survival rate for glioblastoma patients with prior bevacizumab exposure treated with everolimus and sorafenib at the maximum tolerated dose as determined in the phase I study.
- 6 month progression free survival rate for AG patients with no prior bevacizumab exposure treated with everolimus and sorafenib at the maximum tolerated dose as determined in the phase I study.

1.1.2.2 Secondary endpoints:

- Time to progression and overall survival for recurrent malignant glioma patients (Group A, Group B, and Group C) treated with everolimus and sorafenib measured from time of study enrollment.
- Objective response rate for recurrent malignant gliomas (Group A, Group B, and Group C) treated with everolimus and sorafenib
- Patient related outcome measures

To evaluate the occurrence of symptoms and correlate to disease progression and tolerance to treatment using the MD Anderson Symptom Inventory-Brain Tumor Module (MDASI-BT) self-reporting tool. This will include:

- To evaluate longitudinal changes in symptom measures and determine the impact of the therapy on these parameters.
- To measure symptom burden over the course of therapy to evaluate differences between patients individual symptom severity, overall mean symptom severity, and difference in scores on the interference items between responders and non-responders.
- To describe the variability of symptom severity longitudinally over the treatment course and follow-up period.

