5.2 RESPONSE CRITERIA

The primary efficacy endpoint for BTTC studies will be progression free survival (PFS) at six months from patient registration for bevacizumab naïve patients and at 3 months for patients with prior bevacizumab treatment. However, objective response status should be measured and recorded.

All measurements will be performed on the axial MRI T1 post contrast images when possible, although coronal images may be used if axial is not optimal for measurements (or CT post contrast if MRI is contraindicated). The same plane should be used for all measurements. Tumor size is defined as the largest (contrast enhancing) cross sectional area (largest cross-sectional diameter x largest diameter perpendicular to it).

- Evaluable for toxicity: All patients will be evaluated for toxicity from the time of their first treatment with Sorafenib or Everolimus.

- Evaluable for objective response: Only those patients who have measurable disease present at baseline, have received at least one cycle of therapy, and have had their disease re-evaluated will be considered evaluable for response. These patients will have their response classified according to the definitions stated below. (Note: Patients who exhibit objective disease progression prior to the end of cycle 1 will also be considered evaluable.)

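### Section 7.2 names no interval for PFS3, Group B's primary endpoint, and the Kaplan-Meier interval it plans for six-month PFS fails when no patient succeeds

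*Combined protocol and SAP*

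**What the plan says.** Section 7.2 has one sentence on estimating the landmark rate: "Six-month Progression Free Survival (PFS) will be estimated using Kaplan-Meier estimates and associated two-sided 95% confidence intervals". It names no form of interval, no method for a count of zero, and no other landmark. The sentence before it plans Kaplan-Meier curves for time to progression and overall survival.

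The same section then sets two Simon two-stage designs that are decided by counts.
- Group A: nine patients enter the first stage. The rule for continuing is "If two or more patients are progression-free at 6 months (PFS6), an additional 25 patients will be accrued", and promise is declared "If 9 or more out of 34 have PFS6".
- Group B: 14 patients first, 18 more if at least one is progression-free at three months, then "If 2 or more out of 32 have PFS3, then the study will be declared promising".

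Group B's endpoint is at three months, not six. Section 1.1.2 lists as primary the "3 month progression free survival rate for glioblastoma patients with prior bevacizumab exposure", and Section 5.2 repeats that the endpoint is "at 3 months for patients with prior bevacizumab treatment". Section 1.2 puts PFS after bevacizumab failure at roughly 0% at both three and six months. In the cohort table of Section 2.4, Group B is the only cohort not marked closed.

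**The concern.** There are two gaps. First, Group B has a decision rule for its primary endpoint but no planned estimate or interval for it. Second, the one method that is planned fails at zero successes, and these designs make that result likely. Group B can stop early only on 0/14, and the background section leads one to expect rates near zero.

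What is at stake is the reported precision. After 0/14, a Kaplan-Meier interval of 0-0% would suggest certainty that nobody benefits, and an undefined interval would leave the primary result with no measure of uncertainty. The data in fact leave rates up to about 23% open.

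**Working it through.** **Inputs (Section 7.2).** Group A: n1 = 9, continue if at least 2 succeed, n = 34, promising if at least 9, null 15%, alternative 35%. Group B: n1 = 14, continue if at least 1 succeeds, n = 32, promising if at least 2, null 1%, alternative 12%. Stated error is 5% and stated power 80% in both.

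**1. Reproduce the designs.** P(promising) = Σ over continuing x1 of b(x1; n1, p) × P(Bin(n2, p) ≥ r − x1).
- Group A: 0.047 at 15%, 0.811 at 35%.
- Group B: 0.029 at 1%, 0.801 at 12%. The first can be checked by hand: P(Bin(32, 0.01) ≥ 2) − 0.99^14 × P(Bin(18, 0.01) ≥ 2) = 0.0407 − 0.8687 × 0.0138 = 0.0287.

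A search for the optimum design at 5% error and 80% power returns exactly these two designs. The stated 5% and 80% are met as bounds.

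**2. Probability of no success.** Zero successes can occur only at the first stage, because a cohort that continues already has at least one.
- Group B, (1 − p)^14: 0.99^14 = 86.9%; 0.95^14 = 48.8%; 0.88^14 = 16.7%.
- Group A, (1 − p)^9: 0.85^9 = 23.2%; 0.65^9 = 2.1%.

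**3. What Kaplan-Meier gives there.** Without censoring before the landmark, the estimate is S = x/n and Greenwood's variance is S(1 − S)/n. At S = 0 the variance is 0, so the plain interval is 0-0%. The log and log-log forms need log(0) and are undefined; software prints 0-0% or nothing. Exact (Clopper-Pearson) upper 95% limits are 1 − 0.025^(1/14) = 23.2% for 0/14 and 1 − 0.025^(1/9) = 33.6% for 0/9.

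**4. Coverage over the two-stage design.** All outcomes were enumerated and a collapsed interval counted as a miss. Coverage then cannot exceed 1 − P(no success), whichever Greenwood form is used.

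| Group, true rate | P(no success) | Ceiling | Plain | Log | Log-log | Clopper-Pearson |
|---|---|---|---|---|---|---|
| B, 1% | 86.9% | 13.1% | 13.1% | 10.3% | 10.3% | 99.7% |
| B, 5% | 48.8% | 51.2% | 50.8% | 49.3% | 49.3% | 98.0% |
| B, 12% | 16.7% | 83.3% | 79.0% | 80.1% | 82.2% | 98.9% |
| A, 15% | 23.2% | 76.8% | 75.6% | 72.1% | 74.8% | 97.9% |
| A, 35% | 2.1% | 97.9% | 82.6% | 92.5% | 94.5% | 94.5% |

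The Group B rows describe what would happen if the six-month method were carried over to PFS3, since no PFS3 interval is planned.

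**5. Source of the loss.** Among trials with at least one success, the plain interval covers 98.4% (A, 15%) and 99.8%, 99.1% and 94.9% (B at 1%, 5%, 12%). Clopper-Pearson also takes no account of the stages, yet it keeps its coverage. The zero counts therefore explain most of the loss. The 82.6% for Group A at 35% is particular to the plain form.

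**The case against.** The strongest reply is that nothing decided in the trial depends on this interval. Promise is declared by count, the designs are valid, and after 0/14 the cohort stops whatever interval is printed. That stands, and it makes this a reporting point.

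It can also be said that Kaplan-Meier curves for time to progression are planned for all groups, so a three-month value can be read off, and that an unnamed interval form leaves room for a method that handles zero. Both are possible, but neither is specified. Kaplan-Meier does handle censoring, which a simple proportion does not. However, if all 14 patients are seen to progress by three months, the estimate is zero regardless, and the Simon counts already need a status for every patient.

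Two stronger readings are tempting, and the documents support neither.
- *Ignoring the two stages is what ruins coverage.* Step 5 shows otherwise. The raw proportion is somewhat biased by the early stop (−3.6 points in Group A at 15%, −1.1 in Group B at 12%), but an unadjusted exact interval still covers adequately.
- *The 95% interval contradicts the go decision at the boundary.* This depends on a form that the plan does not name. At 2/32 (null 1%), log-log gives 1.1-18.1% and log 1.6-23.9%, both excluding the null; only the plain form includes it. At 9/34 (null 15%), log gives 15.1-46.4% and excludes the null, while plain (11.6-41.3%) and log-log (13.2-41.8%) include it. Exact two-stage 95% intervals also include both nulls (0.9-24.4% and 13.4-49.5%). Any mismatch largely reflects a two-sided 95% interval set beside a one-sided 5% test, which is a common convention.

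**Conclusion.** The point holds as a reporting defect with two parts. The absence of a PFS3 estimate and interval follows from the text alone. The failure at zero successes holds for the plain, log and log-log Greenwood intervals. It would arise in 86.9% of Group B trials at the design's own null and in 23.2% of Group A trials at theirs.

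The coverage figures (10-13%, about 50% and 79-82% in Group B at 1%, 5% and 12%; 72-76% in Group A at 15%) rest on three assumptions: no censoring before the landmark, a collapsed interval counted as a miss, and, for Group B, the six-month method applied at three months. The decision rules, type I error and power stand as stated. A general conflict between interval and decision should not be inferred, nor should a need for a two-stage adjustment.

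**What to change.** In Section 7.2, name PFS6 for Group A and PFS3 for Group B. Report each as a landmark proportion, on the same patients and success counts as the Simon decision, with an exact two-sided 95% interval.

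Clopper-Pearson is adequate: its coverage here is 94.5-99.7% over true rates of 10-35% in Group A and 1-20% in Group B. An exact two-stage interval is an acceptable alternative, and a 90% level to match the one-sided 5% test is optional. Keep the Kaplan-Meier curves as descriptive, including for patients who are censored.

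The cost is a sentence or two of wording and a few lines of code. Intervals are slightly wider than, for example, the log-log form: 0.8-20.8% against 1.1-18.1% at 2/32, and 12.9-44.4% against 13.2-41.8% at 9/34. Sample size, decision rules and patient procedures do not change.

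### The phase II toxicity stopping table holds only if all 82 patients enrol; with the two Simon stage-1 stops, its stopping probabilities at 40% and 50% toxicity and its average sizes are too high

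*Combined protocol and SAP*

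**What the plan says.** All of this stands in section 7.2, Phase II Component.

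- **Toxicity monitoring.** The plan states "we will monitor the toxicity based on the combined data from the above three cohorts with a total sample size of 82". The looks are fixed: "We will monitor the toxicity when the accrual is 5, 10, 20, 35, 50 and 65". Accrual ends "if the posterior probability of toxicity greater than 0.3 is greater than 0.95", with a Beta(0.6, 1.4) prior. The resulting boundary is 4/5, 6/10, 10/20, 16/35, 21/50 and 26/65.
- **The table** ("Operating characteristics of the proposed stopping rule"). At true toxicity 0.2, 0.3, 0.4 and 0.5, the stopping probability is 1.4%, 14.1%, 64.6% and 97.2%. The average number treated is 82, 74.9, 49.9 and 24.9.
- **Group A.** The maximum is 34, with 9 in stage 1: "If two or more patients are progression-free at 6 months (PFS6), an additional 25 patients will be accrued". The null PFS6 is 15% and the target 35%.
- **Group B.** The maximum is 32, with 14 in stage 1 and 18 more only if at least one patient reaches PFS3: "We will halt registration after 14 patients until at least 1 patient is progression free at 3-months". The null PFS3 is 1% and the target 12%.
- **Group C.** It has 16 patients and no efficacy stop.

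The toxicity paragraph does not mention the two efficacy stops, and it does not say that the table is conditional on both cohorts passing stage 1.

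**The concern.** The figure 82 is the sum of three maxima (34 + 32 + 16). Two of them are reached only if an efficacy rule is met. If either cohort closes after stage 1, planned enrolment ends before the look at 65. If both close, it also ends before the look at 50. A table that counts all six looks therefore credits the toxicity rule with looks that may not occur.

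A safety committee or IRB reads the 64.6% and 97.2% as the chance that this trial's rule will detect an overly toxic regimen, and reads the average sizes as expected exposure. If those figures describe a different enrolment pattern, the reader is misinformed about both, and most so when the regimen is inactive.

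**Working it through.** **Step 1. Boundary.** At each look n, take the smallest count x with Pr(toxicity > 0.3) > 0.95 under Beta(0.6 + x, 1.4 + n − x). For n = 5, x = 4 gives 0.975 and x = 3 gives 0.875. For n = 65, x = 26 gives 0.952 and x = 25 gives 0.921. Over all six looks the result is 4, 6, 10, 16, 21, 26, exactly as stated.

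**Step 2. The plan's table.** An exact binomial recursion over the six looks, with enrolment always running to 82, gives:

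| True toxicity | Stop, stated | Stop, exact N = 82 | Average, stated | Average, exact N = 82 |
|---|---|---|---|---|
| 0.2 | 1.4% | 1.3% | 82 | 81.0 |
| 0.3 | 14.1% | 14.0% | 74.9 | 74.1 |
| 0.4 | 64.6% | 64.4% | 49.9 | 49.7 |
| 0.5 | 97.2% | 97.1% | 24.9 | 24.8 |

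The stopping probabilities agree within 0.2 points and the averages within one patient. The table is the full-enrolment calculation.

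**Step 3. Possible totals.**
- Both stop: 9 + 14 + 16 = 39.
- Only A stops: 9 + 32 + 16 = 57.
- Only B stops: 34 + 14 + 16 = 64.
- Neither stops: 34 + 32 + 16 = 82.

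**Step 4. Chance of a stage-1 stop.**
- A stops with 0 or 1 success in 9. At 15%: 0.85^9 + 9 × 0.15 × 0.85^8 = 0.599. At 35%: 0.65^9 + 9 × 0.35 × 0.65^8 = 0.121.
- B stops with 0 successes in 14. At 1%: 0.99^14 = 0.869. At 12%: 0.88^14 = 0.167.

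With both at null, the chances of 39, 57, 64 and 82 are 52.1%, 7.9%, 34.8% and 5.3%.

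**Step 5. Stopping probability by final size.** At 40% toxicity the six looks contribute 0.0870, 0.1059, 0.1201, 0.1019, 0.1256 and 0.1037.
- N = 39 uses the first four looks: 41.5% (81.0% at 50% toxicity).
- N = 57 or 64 uses five: 54.0% (92.4%).
- N = 82 uses all six: 64.4% (97.1%).

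**Step 6. Average over the Simon outcomes.** With both at null and 40% toxicity: 0.0526 × 0.6442 + (0.0787 + 0.3480) × 0.5405 + 0.5208 × 0.4149 = 48.1%. The same weighting gives:

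| Scenario | P(82) | Stop at 0.2 / 0.3 / 0.4 / 0.5 | Average size at 0.2 / 0.3 / 0.4 / 0.5 |
|---|---|---|---|
| Both null | 5.3% | 1.3 / 11.4 / 48.1 / 86.7% | 50.8 / 47.4 / 36.5 / 22.6 |
| A null, B target | 33.4% | 1.3 / 12.7 / 56.2 / 92.8% | 63.3 / 58.5 / 42.4 / 23.9 |
| A target, B null | 11.5% | 1.3 / 12.3 / 53.9 / 91.8% | 62.6 / 58.0 / 42.5 / 24.0 |
| Both target | 73.2% | 1.3 / 13.5 / 61.4 / 95.6% | 75.1 / 68.9 / 47.3 / 24.6 |
| Stated | – | 1.4 / 14.1 / 64.6 / 97.2% | 82 / 74.9 / 49.9 / 24.9 |

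P(82) is the chance before any toxicity stop. The calculation uses one common toxicity rate, independent of progression. Group C fills to 16 and nobody is replaced.

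**The case against.** There is a good case on the other side, and much of it stands.

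- **The premise is stated.** The paragraph names a total of 82, and operating characteristics at the maximum size are a familiar convention. On that premise the table is essentially right, so it is not a calculation error. But naming 82 does not tell the reader that the efficacy stops have been left out.
- **A reader might infer that 82 patients are unlikely in general.** The documents do not support that. At both target rates the chance is 73.2%, and the stopping probabilities then differ from those stated by about 3 points or less. The gap of about 16 points belongs to one corner: both cohorts at null and toxicity at 40%.
- **A reader might infer that patients are less well protected than claimed.** That does not follow either. The toxicity rule stops less often partly because futility has already ended accrual. With both at null, average exposure at 40% toxicity is 36.5 patients, against 49.7 at fixed N = 82. At 50% it is 22.6, against 24.8.
- **Replacement blurs the figures.** Section 5.2.7 replaces inevaluable patients, and section 5.2 counts every treated patient for toxicity. One replacement would bring a trial of 64 to the look at 65. If that happened whenever only B stops, the figure at 40% toxicity would be 51.7% instead of 48.1% (both null), and 61.8% instead of 53.9% (A target, B null). So it cannot be said that the look at 65 occurs only if both cohorts reach stage 2. No replacement rate is given.
- **Section 2.4 lists Groups A and C as closed.** Group A's size is therefore already fixed, but it is not reported. If it filled to 34 (an assumption), the figure at 40% toxicity is 55.4% (B null) to 62.7% (B target). This narrows the range but does not correct the table.

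**Conclusion.** The concern holds as a misstated property of the design. The published rows describe a trial that always enrols 82, whereas the trial in section 7.2 may end accrual at 39, 57 or 64.

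The stopping probability is overstated by 3.2 to 16.5 points at 40% toxicity (64.6% against 61.4% and 48.1%). At 50% it is overstated by 1.6 to 10.5 points (97.2% against 95.6% and 86.7%). At 30% the difference is under 3 points, and at 20% there is essentially none. The average size at 20% toxicity is overstated by 6.9 to 31.2 patients (82 against 75.1 and 50.8). Even with full enrolment it is 81.0.

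These sizes rest on independence of toxicity and progression, a full Group C and no replacement. Because of replacement, the figures for a trial in which only B stops are the least firm. The boundaries depend only on the data at each look and not on the final size, so the monitoring rule is sound as written.

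**What to change.** 1. Label the present rows as conditional on full enrolment of 82, that is, on both Group A and Group B passing stage 1.
2. Correct the average at 20% toxicity from 82 to 81.0. The exact averages at the other rates (74.1, 49.7, 24.8) can be entered at the same time.
3. Add rows averaged over the Simon rules for both nulls and both targets, from the table above. Alternatively, add rows for N = 39, 57 and 64 (41.5%, 54.0% and 54.0% at 40% toxicity), which need no efficacy assumption.
4. State the assumptions of independence and no replacement beside the new rows.

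The cost is a short recalculation and a few table rows, and the stated stopping probabilities will look less favourable. The boundaries, sample sizes and conduct of the trial do not change.

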It is not clear which molecular determinants predict responsiveness of tumor cells to everolimus. Molecular analysis has revealed that relative sensitivity to everolimus in vitro correlates with the degree of phosphorylation (activation) of the AKT/PKB protein kinase and the S6 ribosomal protein. PTEN status alone may not be predictive of everolimus relative in vitro sensitivity, however in some cases (i.e., GBM) there is also a correlation with PTEN status (active vs inactive). In preclinical models, the administration of everolimus is associated with reduction of protein phosphorylation in target proteins downstream of mTOR, notably phosphorylated S6 (pS6) and p4E-BP1, and occasionally with an increase in phosphorylation AKT (pAKT).

1.2.5 Rationale for combination therapy:

Preclinical data suggest that blocking more than one target more effectively inhibits tumor growth. (22) Combining everolimus and sorafenib allows targeting of both the PI3K pathway and the RAF-MAPK pathway and in addition targets VEGF and PDGF, other active targets in malignant glioma. Trials of mTOR inhibition (not everolimus) with sorafenib are underway but the dose of the mTOR inhibitor, in particular CCI-779, being used in one of these trials is sufficiently low that it is likely not therapeutic. We believe that the combination of everolimus and sorafenib will be more tolerable, thus allowing therapeutic doses of both. In addition, continuous oral dosing of both may provide a more sustained pathway inhibition.

1.2.6 Rationale for patient outcomes measures:

1.2.6.1 Rationale for the patient-reported outcomes:

This study seeks to establish effective therapies at recurrence and improve on current clinical results in patients with glioblastoma. We hypothesize that using a combination of everolimus and sorafenib will result in improved survival. However, given the intensive nature of this regimen, it will be important to determine whether any determined survival benefit is associated with improvements in symptoms or does a worsening of symptoms offset the increase in survival.

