3.4 QUESTIONNAIRES

The MDASI-BT will be utilized for this portion of the study. Full instruments are provided in the Appendix 13.4. In addition, information regarding demographics and treatment history will be collected as part of the larger study and used in this analysis.

The MDASI-BT consists of 23 symptoms rated on an 11-point scale (0 to 10) to indicate the presence and severity of the symptom, with 0 being “not present” and 10 being “as bad as you can imagine.” Each symptom is rated at its worst in the last 24 hours. Symptoms included on the instrument include those commonly associated with cancer therapies, those associated with increased intracranial pressure, and those related to focal deficits. The questionnaire also includes ratings of how much symptoms interfered with different aspects of a patient’s life in the last 24 hours. These interference items include: general activity, mood, work (includes both work outside the home and housework), relations with other people, walking, and enjoyment of life. The interference items are also measured on 0 - 10 scales. The average time to complete these instruments is 5 minutes. The MDASI-BT has been translated into 18 languages ([24](#), [25](#)).

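### Section 7.2 reverses the direction of the 2-point MDASI-BT change rule: a rise in mean symptom severity or interference is labelled improvement, although every item is scored higher = worse

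*Combined protocol and SAP*

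**What the plan says.** The patient-reported outcomes part of section 7.2 classifies a difference of at least 2 points as the minimum clinically meaningful change in the symptom severity and symptom interference measures. It then illustrates the direction in one sentence with two halves. On a rise in score, the plan states: "an increase of 2 points or more would mean a moderate improvement". The other half deals with a fall in score and takes the opposite view: "a decrease of 2 points or more would be interpreted as moderate worsening". The sentence after that covers single items and runs the other way: "For individual symptoms, a rise in a symptom score means deterioration", and a lower score is improvement.

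The summary measures are described earlier in the same section as means: mean core symptom severity, mean MDASI-BT severity and mean symptom interference. Section 3.4 describes the symptoms as "rated on an 11-point scale (0 to 10) to indicate the presence and severity of the symptom", with 0 meaning absent and 10 the worst imaginable, and says that the interference items also use 0 to 10 scales. The form in Appendix 13.4 prints the anchors for both parts.

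Section 1.1.2.2 lists among the secondary endpoints "To evaluate longitudinal changes in symptom measures and determine the impact of the therapy on these parameters".

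**The concern.** A mean of items has the same direction as the items. If each item is worse when higher, so is the mean. Section 7.2 nevertheless reads the mean one way and the items that make it up the other way, in consecutive sentences.

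This matters because of why the questionnaire is in the trial. Section 1.2.6.1 says that it should show whether any survival benefit is "associated with improvements in symptoms or does a worsening of symptoms offset the increase in survival". The 2-point rule is the only statement in the plan of how large a change in these measures is clinically meaningful, and the sentence after it is the only one in 7.2 that gives the summary measures a direction. Applied as written, it would report symptom worsening on treatment as improvement, and relief as worsening.

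**Working it through.** There is no sample size, power or error rate to reproduce here. The check is to read the direction of each scale and then apply the rule to a simple change.

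**Step 1: direction of the items (Appendix 13.4).**
- Part I, items 1 to 22: 0 means that the symptom was absent, 10 that it was as bad as imaginable. Higher is worse.
- Part II, items 23 to 28: 0 means no interference, 10 complete interference. Higher is worse.
- Count: 22 + 6 = 28 printed items. All 28 are higher = worse and none is reversed.

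Section 3.4 gives the same direction for the symptoms. The plan to report high scores in 7.2, "The proportion of patients rating their symptoms to be 7 or greater (on a 0-10 scale) will also be reported", fits a scale on which high is severe.

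**Step 2: direction of the summary measures.** Section 7.2 calls them means and mentions no reversal or rescaling. With k items each changing by d points, the mean changes by (k × d)/k = d. The direction is kept, for the full set of items or for any subset such as the core symptoms.

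**Step 3: apply the rule.** Assume, for illustration only, that every item moves from 3 to 5.
- Mean severity: (22 × 2)/22 = 44/22 = +2.0.
- Mean interference: (6 × 2)/6 = 12/6 = +2.0.
- Section 3.4 speaks of 23 symptoms where the form prints 22. With 23 the severity result is 46/23 = +2.0, so the count does not matter.

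A move from 5 to 3 gives −2.0 in both. The labels are then:

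| Change in mean | 7.2 rule for the measures | 7.2 sentence on individual symptoms | Printed anchors |
|---|---|---|---|
| Severity +2.0 | moderate improvement | deterioration | worse |
| Interference +2.0 | moderate improvement | not covered | worse |
| Severity −2.0 | moderate worsening | improvement | better |
| Interference −2.0 | moderate worsening | not covered | better |

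The rule disagrees with the anchors in all four rows. For severity it also disagrees with its own next sentence.

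**Step 4: look for a reading that rescues the rule.**
- *A summary score on which higher is better.* None is defined; the measures are plain means.
- *Change taken as baseline minus follow-up.* Not stated, and the sentence speaks of an increase or decrease in points.
- *A deliberate contrast between symptom items and a function-type scale.* The form has no scale on which higher is better, and mean severity averages the same symptoms.

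None of the three has support in the text.

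**Step 5: apply the corrected direction.** With the two words exchanged, +2.0 reads as worsening and −2.0 as improvement in all four rows. This agrees with the anchors and with the individual-symptom sentence. The 2-point threshold is unchanged.

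**The case against.** The best defence does not dispute the sign; it says that the error is small and self-evident. The sentence that sets the threshold has no direction, and only the example after it is reversed. For severity, the next sentence gives the right direction. For interference, the printed form leaves no doubt about what a high score means. A careful analyst would notice, and the outcomes are secondary and descriptive.

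Much of this stands, and it limits the size of the point. It does not remove it. The example is the only place where 7.2 tells the analyst how to read a rise or fall in the summary measures, and for interference nothing else in that section corrects it. A prespecified rule should not come out right only when it is ignored.

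Two stronger readings are tempting, and the documents do not support them.
- A reader might infer that the comparison of responders with non-responders is reversed as well, since section 1.1.2.2 also lists "overall mean symptom severity, and difference in scores on the interference items between responders and non-responders". That analysis estimates a difference in means between two groups. The faulty sentence labels increases and decreases and does not set the direction of a between-group difference, so an effect there is not shown.
- A reader might infer that the 2-point rule should also govern single items. Section 7.2 gives individual symptoms a direction but no threshold. Extending the cut to items would add a rule that the plan does not contain.

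**Conclusion.** The sign is wrong as written, and confidence in that is high. All 28 printed items are higher = worse, no reverse scoring is defined, and 7.2 contradicts itself on severity in adjacent sentences. Followed literally, the rule would mislabel every longitudinal change of 2 points or more in mean severity or mean interference, and so would reverse the answer to the question posed in section 1.2.6.1.

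The defect has no numerical size beyond that. It changes labels, not estimates: the means are computed correctly whatever they are called, and the progression-free survival decision rules and the toxicity stopping rule are untouched. A reader might infer that the trial's main conclusions are at risk; they do not depend on this sentence. Nor do the documents show that any result has been or will be mislabelled.

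The conclusion rests on the printed form being the one used and on the summary measures being plain means, as 7.2 describes them. The scores in the working are illustrative and only show the direction. The point should be fixed because it concerns a stated interpretation rule for a secondary endpoint and the correction is trivial.

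**What to change.** In the patient-reported outcomes part of section 7.2, exchange the words improvement and worsening in the example sentence. An increase of 2 points or more is then moderate worsening, and a decrease of 2 points or more is moderate improvement. Keep the scope of the sentence to the symptom severity and symptom interference measures, keep the 2-point threshold, and leave the following sentence on individual symptoms unchanged.

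The cost is a two-word correction. No data, visit, analysis method or sample size changes.
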